This is a concurrently controlled trial. Study participants will be randomly selected from those participating in the ongoing, longitudinal +BHN study at 2 sites in Montreal (The Montreal Chest Institute and L'Actuel Medical Clinic). This CIHR Team Grant-supported observational, prospective cohort study is enrolling consecutive patients attending 5 HIV clinics across Canada for a total sample of 900, followed every 9 months for 27 months. Inclusion criteria are: age 35 y or older, HIV infection for at least 1 year, able to communicate in English or French and capable of providing informed consent. Exclusions are presence of dementia, life expectancy < 3 y, other neurological disorder including active opportunistic CNS infection, psychotic disorder, current substance dependence or abuse, and Hepatitis C requiring interferon therapy during the study period. Montreal sites will enroll 350 participants, which should provide an adequate pool for recruitment to this sub-study.

The GMT intervention will be tested in a randomly selected sub-group (N=30) of this cohort who meet the following additional criteria: over age 45, subjective complaints of cognitive difficulties, and performance on objective computerized cognitive tests that falls at or below the 50th percentile of performance in the cohort as a whole (as measured by the cohort study's primary outcome, a combination of self-report and performance items called the Brief Cognitive Ability Measure [B-CAM] (17)). The concurrent control group will be comprised of those eligible for GMT but not randomly selected.

Procedure

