Subject Identification Number Assignment

Subject Identification (ID) numbers assigned for the core platform will be used for this sub-study.

DETAILS OF STATISTICAL ANALYSIS

Analysis and Sample Size

The feasibility and acceptability of the GMT will be evaluated in the whole group (N=30) based on the proportion of GMT sessions attended, the proportion of the homework completed, and the overall level of satisfaction with the program, as determined by an anonymous questionnaire filled out by the participants at the end of the intervention.

The potential impact on cognition of GMT will be evaluated in two ways: (i) a within-person analysis of change in cognitive outcomes after all persons have completed the GMT program; and, for exploratory purposes, (ii) a between group comparison contrasting change in cognitive outcomes between the GMT group and the concurrent control group assessed in the main study.

For all analyses, the B-CAM (performance measure) will be the primary cognitive outcome and a global outcome response will be based on changes in the B-CAM and on four secondary cognitive outcome measures: SART, Tower of London, Dysexecutive Questionnaire-DEX and PDQ.

For the within-person analysis, change from pre-to post will be calculated for each person and a 95% confidence interval (CI) around the mean change will be calculated. A 95% CI that excludes 0 indicates statistically significant change. A sample size of 30 will provide 80% power to detect an average standardized response mean (effect size for change) of 0.38, within the reported range for GMT in other conditions. However, average change is not very interpretable as this average change can occur in many ways including no change for a lot of people and large change for a few, or even deterioration for some. To provide a more interpretable estimate of treatment impact, an overall effect will also be reported, based

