on the proportion of individuals who improved at least 0.5 SD on one of the cognitive outcome measures. A change of 0.5 SD is considered clinically relevant (21). For this analysis, generalized estimating equations (GEE) will be utilized to adjust for a possible correlation between the different measures. The outcome will be the binary response for each of the five cognitive outcomes, and the analysis yields an estimated charge proportion adjusted for non-independence. Having five outcome measures increases the number of observations available for analysis by a factor of 1.8, termed the design effect. The design effect (22) is a function of the number of measures (here m-1) and the correlation between measures (estimated at 0.2). Hence the number of observations effectively available for analysis is 30 x 1.8 or 54. With this sample size, the 95% CI will exclude a low responder proportion (20%) as long as the responder proportion is greater than 28% (www.vassarstats.net).

For the between-group analysis, 30 people in the intervention group and a concurrent control group of 100 (with five outcome measures, the effective sample size is inflated by the design effect of 1.8). Thus, using all measures, the sample would provide 80% power to detect an effect size of 0.4 (0.4 of a SD). For this analysis, generalized estimating equations (GEE) for a continuous outcome will be utilized to adjust for a possible correlation between the different measures. Each measure will be transformed onto a 0 to 100 scale for permit a global intervention effect to be estimated.

REFERENCES

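### Thirty people give about 52% power, not 80%, to detect a standardized response mean of 0.38; the detectable value at n = 30 is 0.53

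*Combined protocol and SAP*

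**What the plan says.** All references are to the combined protocol and SAP. Under Details of Statistical Analysis, Analysis and Sample Size, the within-person analysis is described as follows: "change from pre-to post will be calculated for each person and a 95% confidence interval (CI) around the mean change will be calculated". The significance rule comes next: "A 95% CI that excludes 0 indicates statistically significant change". The power claim follows: "A sample size of 30 will provide 80% power to detect an average standardized response mean (effect size for change) of 0.38". The plan adds that this effect lies within the range reported for Goal Management Training (GMT) in other conditions.

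The same section makes B-CAM the primary cognitive outcome for every analysis and labels the between-group comparison exploratory. Study Design gives the size of the treated group: "The GMT intervention will be tested in a randomly selected sub-group (N=30) of this cohort".

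A larger number appears only afterwards, in the paragraph on the responder analysis by generalized estimating equations. Five outcomes with an assumed correlation of 0.2 are said to multiply the available observations by 1.8: "Hence the number of observations effectively available for analysis is 30 x 1.8 or 54".

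**The concern.** A one-sample test on 30 changes has a standard error of 1/√30 = 0.18 SD. An effect of 0.38 is then only about two standard errors from zero, which is close to the significance threshold itself. Power at such an effect is near one half, so 80% cannot be right for a single outcome.

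This matters because the within-person comparison is the main efficacy reading in the plan. Background information argues that later steps are pointless if established rehabilitation methods show no efficacy, and Clinical Significance says that the results will inform a full randomized trial. A reader who believes the study had 80% power for 0.38 could give a null B-CAM result more weight than it can bear. The reassurance that the detectable effect is plausible for GMT is also attached to 0.38, not to the effect that 30 people can detect.

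**Working it through.** **Inputs, all from Analysis and Sample Size**

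- n = 30 people, one change score each.
- Two-sided α = 0.05, from the 95% confidence interval rule.
- Target power 80%.
- SRM = 0.38. An SRM is the mean change divided by the SD of change, so no separate SD or pre-post correlation is needed.

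**Formulas**

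- Exact power: noncentral t with n − 1 degrees of freedom and noncentrality SRM × √n.
- Normal approximation: power = Φ(SRM × √n − 1.960); detectable SRM = (1.960 + 0.842)/√n = 2.80/√n.

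**1. Trying to reproduce the stated figure at n = 30**

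- Noncentrality = 0.38 × √30 = 2.08. The critical t on 29 degrees of freedom is 2.05.
- Exact power = 52.1%. A simulation gave 52.4%.
- Normal approximation: Φ(2.081 − 1.960) = 54.8%.
- SRM detectable with 80% power: 0.529 exact; 2.80/√30 = 0.512 by normal approximation.
- People needed for 0.38 at 80% power: exact power is 79.8% at 56 and 80.5% at 57, so 57. The normal approximation gives (2.80/0.38)² = 54.4, so 55.

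The printed 80% is not reproduced. The shortfall is 80 − 52 = 28 percentage points, and the detectable SRM is understated by 1 − 0.38/0.529 = 28%.

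**2. Other readings**

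| Reading | SRM detectable with 80% power | Power at 0.38 |
|---|---|---|
| n = 30, two-sided 5% (as written) | 0.529 | 52.1% |
| n = 30, one-sided 5% | 0.465 | 65.1% |
| n = 54, two-sided 5%, exact t | 0.388 | 78.3% |
| n = 54, two-sided 5%, normal | 0.381 | 79.7% |
| n = 60, two-sided 5%, exact t | 0.368 | 82.5% |
| n = 30, mean of five measures, correlation 0.2 | 0.318 | 91.8% |

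The n = 54 row under the normal approximation matches the printed pair of 0.38 and 80%.

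For the last row, take five measures with equal SDs of change and correlation 0.2. The variance of their mean is (1 + 4 × 0.2)/5 = 1.8/5 = 0.36 of that of one measure. The detectable average SRM is therefore 0.529 × √0.36 = 0.318. The equivalent effective number is 30 × 5/1.8 = 83, not 54: the 1.8 is a variance inflation factor, and it divides the 150 observations.

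**3. Attrition**

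The plan gives no allowance for dropout. Taking 25 completers purely as an illustration, the detectable SRM is 0.584 and power at 0.38 is 44.6%.

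**The case against.** The best defence rests on the word average. An SRM is already a mean, so an average SRM could mean one averaged over the five outcomes, and the paragraph before it sets up a global response over those five. On that reading, at the plan's correlation of 0.2, 30 people would have about 92% power for 0.38, and the claim would err on the cautious side. At a correlation of 0.4 the detectable average would be 0.529 × √(2.6/5) = 0.382, almost the printed value.

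Part of this stands: the sentence could be clearer, and a pooled analysis would be better powered than B-CAM alone. But the sentence does not mention pooling, and the next one uses average change to mean an average over people. The plan assumes a correlation of 0.2, at which the pooled value is 0.32, not 0.38. The primary outcome also remains a single measure.

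Other objections have less force:

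- The documents do not say that 54 was used. This is correct, and it is offered here only as the likely explanation.
- The Protocol Summary gives a sample size of 60. With 60 the detectable SRM would be 0.37, near the printed value, but the sentence says 30, as does Study Design. That conflict needs its own resolution.
- This is a pilot whose first objective is feasibility, no decision rule uses 0.38, and the reported interval will show the imprecision. All true, and it limits the harm. Evidence of effect is nevertheless a stated objective, and the plan chose to make a numerical power claim.

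**Conclusion.** The concern holds. For the mean change on one outcome, B-CAM included, 30 people give 52% power at an SRM of 0.38. They give 80% power only at 0.53 (0.51 by normal approximation), and 0.38 would need 57 people. This rests on the plan's own inputs and on roughly normal change scores with no losses; any dropout makes it worse. No reading tested that keeps both 30 people and the plan's stated assumptions reproduces 80% power at 0.38. Whether 0.53 lies within the range reported for GMT cannot be judged from the documents, which do not give that range. The figure should be corrected before the plan is relied on.

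**What to change.** Replace the power sentence with wording such as: With 30 participants, the within-person analysis has 80% power to detect an SRM of 0.53 on B-CAM (two-sided 5%, one-sample t test); power for an SRM of 0.38 is 52%.

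Then:

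- State the expected number of completers and give the detectable SRM for that number.
- Recheck the claim about the reported range for GMT against 0.53, and cite the range.
- If 0.38 was meant for a pooled five-measure analysis, say so, and recompute it with the correct effective number (30 × 5/1.8 = 83 at a correlation of 0.2).

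The cost is a change of wording. The stated figure becomes less favourable, but no participants are added and no endpoint or analysis changes.

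### The responder summary offered as treatment impact is worded as two different proportions, its SD is unnamed, and it is not compared with the controls

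*Combined protocol and SAP*

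**What the plan says.** All of this is in the combined protocol and SAP. Under Analysis and Sample Size, the within-person analysis reports mean change with a 95% CI. Because a mean can hide who changed, the plan adds an overall effect based "on the proportion of individuals who improved at least 0.5 SD on one of the cognitive outcome measures". Half an SD is called clinically relevant, but the SD is not identified.

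The same paragraph then specifies the model: "The outcome will be the binary response for each of the five cognitive outcomes", with GEE used to allow for correlation between measures (estimated at 0.2) and to return a single proportion. On precision it says "Hence the number of observations effectively available for analysis is 30 x 1.8 or 54", and that "the 95% CI will exclude a low responder proportion (20"%) once the responder proportion is above 28%.

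Controls enter through a second, exploratory analysis: "a between group comparison contrasting change in cognitive outcomes between the GMT group and the concurrent control group assessed in the main study". For that comparison, "generalized estimating equations (GEE) for a continuous outcome will be utilized".

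Under Study Design, GMT participants must show "performance on objective computerized cognitive tests that falls at or below the 50th percentile of performance in the cohort as a whole". The score used for this is the B-CAM, which is also the primary cognitive outcome. On the comparison group: "The concurrent control group will be comprised of those eligible for GMT but not randomly selected".

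**The concern.** An analyst could follow either sentence. The first gives one binary result per person with 30 people. The second gives an average response rate per measure over 150 binary results. With five chances to cross the line, the first is far higher than the second for the same data. If it were reported beside the 20% written for the second, a trial with no effect could look strongly positive.

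Two further gaps affect even the second definition. The B-CAM is used for selection, so its SD in the selected group is narrower than in the cohort, and the meaning of 0.5 SD depends on which is used. In addition, 20% is not described as the rate expected without treatment. Retest noise and regression to the mean after low-score selection both produce apparent responders. The concurrent controls, who could show how many, are not used for this outcome.

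**Working it through.** **Inputs from the plan:** 5 measures, correlation 0.2, 30 GMT participants, 100 controls, cut at 0.5 SD, benchmark 20%. **Assumed, not in the documents:** retest reliability r = 0.7, 0.8 or 0.9; normal scores; no mean change; the 0.2 correlation applied to change scores.

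**1. The plan's own figures.** 1 + (5 − 1) × 0.2 = 1.8 and 30 × 1.8 = 54, as stated. The 28% does not reproduce at 54: 15/54 (27.8%) has a Wilson lower limit of 17.6%, and the smallest count that excludes 20% is 17/54 (31.5%). That is a separate matter, and nothing below depends on the 28%.

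**2. No-effect rate per measure.** In baseline SD units the SD of change is √(2(1 − r)) = 0.775, 0.632, 0.447. The rate is 1 − Φ(0.5/√(2(1 − r))) = 25.9%, 21.5%, 13.2%. It equals 20% at r = 0.82.

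**3. No-effect rate on any of five.** With t = 0.5/√(2(1 − r)) and equal correlation ρ = 0.2, the rate is 1 − ∫Φ((t − √ρ x)/√(1 − ρ))⁵ φ(x) dx.

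| | r = 0.7 | r = 0.8 | r = 0.9 |
|---|---|---|---|
| Per measure | 26% | 21% | 13% |
| Any of five | 70% | 62% | 45% |

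The same formula turns 20% per measure into about 60% any-of-five (67% at correlation 0, 52% at 0.4). The two definitions therefore need different benchmarks.

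**4. Literal definition read against 20%.** With n = 30 the Wilson interval first excludes 20% at 11/30 (lower limit 21.9%). The binomial chance of 11 or more with no effect is about 86% at r = 0.9 and over 99% at r = 0.8 and 0.7. Against the matched benchmark of 59.7%, which needs 24/30, it is about 15%, 3% and under 0.1% at r = 0.7, 0.8 and 0.9.

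**5. GEE definition read against 20%.** Simulated no-effect trials of 30 × 5 give the share whose 95% CI lies wholly above 20%. Each range runs from a Wilson interval with the plan's 54 to a robust-SE logit interval.

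| | r = 0.7 | r = 0.8 | r = 0.9 |
|---|---|---|---|
| B-CAM selection ignored | 12–34% | 1–6% | 0% |
| Selecting B-CAM score is the baseline, cohort SD | 24–51% | 3–12% | 0% |

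The second row raises only the B-CAM rate and leaves the other four measures at step 2. Its r = 0.8 upper end is 12–13% between runs.

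**6. Which SD.** Selection at or below the median leaves an SD of √(1 − 2/π) = 0.603 of the cohort SD. The table gives no-effect rates at r = 0.7/0.8/0.9; in the separate-visit row the selected-group SD is the one at that later visit.

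| | Cohort SD | Selected-group SD | Shift |
|---|---|---|---|
| B-CAM, selecting score is the baseline | 36/29/17% | 47/41/31% | 10–14 points |
| B-CAM, baseline at a separate visit | 26/21/13% | 30/27/22% | 4–9 points |
| Pooled over five, selecting score is the baseline | 28/23/14% | 30/25/17% | 2–3 points |

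The pooled row is (B-CAM rate + 4 × per-measure rate)/5.

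**7. Precision of a control comparison.** The half-width is 1.96√(p(1 − p)(1/30 + 1/100)) = 15.3, 18.5 and 19.6 points at p = 0.17, 0.29 and 0.36. A single proportion of 30 gives 13.4, 16.2 and 17.2.

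**The case against.** The best defence is that everything operational in the paragraph is per measure: the binary outcomes, the GEE, the 54 and the 20%. No any-of-five analysis, sample size or benchmark is given. The opening clause may be loose wording for improvement on a given measure, in which case the repair is one clause. That is a fair reading, and it limits the severity. It does not remove the ambiguity, because the clause counts individuals and no rule links it to the model.

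A reader might infer that the trial would declare success whenever the proportion exceeds 20%. The documents do not support that: the 20% appears in a precision statement with no decision attached, in a pilot seeking preliminary evidence. Nor do they support calling the GEE proportion mostly noise. At r = 0.9 its interval essentially never clears 20% without an effect, at r = 0.8 it does so seldom, and only around r = 0.7 or below is it common. Reliability is not given, so the true position is unknown.

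It can also be said that a controlled comparison already exists. It does, for continuous change, so the trial is not without controls. The gap is confined to the responder outcome.

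**Conclusion.** The concern holds in limited form. One summary has two definitions, and at the plan's own correlation they differ by a factor of about three (20% against about 60%). Taken literally and set against the stated 20%, the first would mislead in about 86% to over 99% of no-effect trials at the assumed reliabilities. Under the GEE definition the risk is much smaller and depends on reliability and on which B-CAM score serves as baseline.

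The unnamed SD matters for the B-CAM responder rate (10–14 points if the selecting score is the baseline, about 4–9 if not). A reader might carry the larger figure over to the pooled result, but there the shift is only 2–3 points in the same-visit case.

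All sizes rest on normal scores, no practice gain and assumed reliabilities. Severity is minor to moderate, because mean change with its CI stands beside this summary in a pilot.

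**What to change.** 1. Delete the any-one-measure definition and keep the GEE per-measure proportion.
2. Name the SD: the cohort baseline SD for B-CAM and any other measure the cohort collects, and the sub-study baseline SD for the rest, saying which is which.
3. State that a proportion above 20% is not evidence of a GMT effect.
4. For B-CAM, and any other measure the controls have, report the GMT-minus-control difference in responder proportion with its 95% CI, labelled exploratory. Use one baseline rule in both groups: the qualifying visit in both, or a later visit in both. If only the controls were anchored at the qualifying visit, regression to the mean would affect them alone (36/29/17% against 26/21/13%), a spurious 4–10 points against GMT. State the retest interval in each group.
5. For measures without control data, report the proportions improving and worsening by 0.5 SD as descriptive only. The Procedure section describes SART, Tower of London and DEX for participants who then begin GMT, so control data on these are not assured.

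The cost is SAP wording, using data already planned. The downsides are a B-CAM difference known only to about ±15–20 points at 30 against 100, an imprecise sub-study SD from 30 people, and a weaker claim. Cohort visits are 9 months apart while GMT retesting falls within 4 weeks of the programme's end, so retest intervals may differ and practice effects may not cancel.

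### The only written within-person analysis that pools the five cognitive outcomes uses changes cut at 0.5 SD and a fixed 20% reference; a pooled estimate on the uncut changes should be added and carry the inference.

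*Combined protocol and SAP*

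**What the plan says.** All of this is in the section on analysis and sample size, under the details of statistical analysis.

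The within-person analysis has two parts. In the first, "change from pre-to post will be calculated for each person and a 95% confidence interval (CI) around the mean change will be calculated", and the plan adds that "A 95% CI that excludes 0 indicates statistically significant change". No pooling over measures is described there. The B-CAM is the primary cognitive outcome, and "a global outcome response will be based on changes in the B-CAM and on four secondary cognitive outcome measures". The power statement is that "A sample size of 30 will provide 80% power to detect an average standardized response mean (effect size for change) of 0.38".

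The second part is an overall effect, reported in addition because the plan regards an average change as hard to interpret. It counts a gain of 0.5 SD as a response, cites a source for the clinical relevance of that cut, and fits a GEE: "The outcome will be the binary response for each of the five cognitive outcomes, and the analysis yields an estimated charge proportion adjusted for non-independence". The five measures are said to raise the 30 people to 54 effective observations (30 x 1.8, correlation 0.2). The plan then says that "With this sample size, the 95% CI will exclude a low responder proportion (20%) as long as the responder proportion is greater than 28" per cent.

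For the exploratory comparison between groups, the same five measures are kept continuous: "For this analysis, generalized estimating equations (GEE) for a continuous outcome will be utilized to adjust for a possible correlation between the different measures". They are first rescaled to 0 to 100.

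The section does not say whether 0.5 SD refers to the baseline SD or to the SD of change. It names no link for the binary GEE and gives no power for it.

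**The concern.** With 30 people, pooling five measures is where the within-person analysis can gain precision, and the plan does this only after cutting each change. A gain of 0.49 SD then counts the same as none, and 0.51 SD the same as 2 SD. The reasons given, interpretability and clinical relevance, support reporting a responder proportion. They do not explain why no pooled estimate on the full scale accompanies it, when the continuous GEE is already specified for the comparison between groups.

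The reference is a second difficulty. A CI that excludes 20% is evidence of improvement only if about 20% would respond with no mean change. That rate depends on the SD that defines the cut, which is not stated. The pilot is meant to inform a full randomized trial, so the pooled result should be both efficient and readable.

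**Working it through.** **Inputs from the plan.** 30 people, five measures, correlation 0.2, two-sided 5% (from the 95% CI), SRM 0.38, cut 0.5 SD, reference 20%.

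**Assumptions added here.** Changes are normal, the SRM is the same on all five measures, and the correlation is exchangeable.

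**1. The plan's own figures.** The detectable SRM at 80% power is (1.96 + 0.84)/√n.
- n = 30: 2.80/5.48 = 0.51. At 0.38 the power is 55% by the normal approximation and 52% by the noncentral t.
- n = 54: 2.80/7.35 = 0.38. At 0.38 the power is 80% (normal) or 78% (t).

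The stated 0.38 is therefore reproduced with the five-measure effective size of 54, and not with 30 people on one measure. The 28% threshold is not reproduced at n = 54: the Wilson lower limit at 28% is 17.8%, and about 30.7% is needed to exclude 20%. These are separate points. They matter here because they suggest that a pooled continuous analysis may have been in mind.

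**2. Responder rate with no effect.** If the cut lies at z SDs of change, the rate at zero mean change is 1 − Φ(z).
- The SD is that of change: z = 0.5, rate 30.9%.
- The SD is the baseline SD, with equal variances and pre-post correlation r: the SD of change is √(2(1 − r)) baseline SDs. With r = 0.7 (assumed), z = 0.5/0.775 = 0.645, rate 25.9%.
- For a rate of exactly 20%, z = 0.842, which needs r of about 0.82. The documents give no r.

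**3. Efficiency of the cut.** Per measure it is φ(z)²/[p(1 − p)], which gives 0.58, 0.55 and 0.49 for these three cuts. Cut scores are less correlated with each other than uncut ones (about 0.11 to 0.12 against 0.2, near no effect), so pooling recovers part of this. Effective observations are 150/(1 + 4 x 0.2) = 83 uncut. They are 150/(1 + 4 x 0.123) = 101 for the 0.5 cut and 150/(1 + 4 x 0.11) = 104 for the 0.842 cut. Pooled efficiency is then about 0.58 x 101/83 = 0.70 and 0.49 x 104/83 = 0.61.

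**4. Power by simulation.** There were 20,000 runs of 30 people x 5 measures, analysed by independence GEE with a person-clustered SE and t on 29 df. The uncut mean is tested against 0. The cut proportion is tested against its own no-effect rate, and the ranges cover the three cuts.

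| SRM | Uncut | Cut, logit | Cut, identity |
|---|---|---|---|
| 0.20 | 43% | 31–33% | 23–30% |
| 0.25 | 60% | 45–48% | 36–43% |
| 0.30 | 75% | 60–63% | 51–58% |
| 0.38 | 92% | 80–83% | 73–80% |

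The loss is 9 to 15 points on the logit scale and 12 to 25 on the identity scale. The identity interval is conservative (upper-tail error 1.3 to 1.8% against a nominal 2.5%; logit 2.2 to 2.4%), so the upper end is not due to the cut alone. With correlation 0.4 the losses are 6 to 12 (logit) and 10 to 22 (identity). By normal approximation at correlation 0.2, the loss shrinks to 3 to 4 points at SRM 0.10 and 3 to 6 at SRM 0.50.

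**5. The fixed 20% reference with zero mean change** (identity scale). The CI lies wholly above 20% in about 63% of runs if the no-effect rate is 30.9%, and in about 22% if it is 25.9%. At SRM 0.38 it does so in 100% and 98% of runs. Under those definitions of SD the comparison signals improvement too readily.

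**The case against.** The strongest reply is that the responder analysis is an addition. The continuous mean change stays, it carries the only stated significance rule, and the B-CAM is named as primary. The proportion answers a different question, namely how many people change by a relevant amount, and its cut is fixed in advance and supported by a citation. All of this stands. A reader might infer that the main within-person test is weakened; the documents do not support that.

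A reader might also infer that the cut throws away most of the gain from five measures. That is not shown. At SRM 0.38 the cut GEE on the logit scale still has 80 to 83% power, against about 52% for a single measure in 30 people.

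Nor can it be said that the plan will tend to miss a real improvement. That outcome presupposes that 20% is the no-effect rate. If the SD is that of change, the error runs the other way, to false positives. No go/no-go rule is tied to the responder proportion, so a misled decision about the full trial is conjecture.

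Finally, the stated SRM of 0.38 fits 54 observations, and the plan calls it an average SRM. A pooled continuous within-person analysis may have been intended. Even so, it is not written, and the power statement has no matching analysis without it.

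**Conclusion.** The point holds in limited form. On the written text, the binary GEE is the only within-person analysis that pools the five outcomes. Against a matched reference, at correlation 0.2 and SRM 0.20 to 0.38, cutting costs about 9 to 15 points of power (logit) or 12 to 25 (identity). These figures rest on normal changes and an equal SRM across measures. The documents fix neither the link nor the SD, so the range is conditional and cannot be derived from the plan alone.

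The fixed 20% is a separate weakness of the same analysis. It corresponds to no effect only under a particular, unstated pre-post correlation, and under one natural reading of the SD it would be excluded in about 63% of runs with no effect. The separate mean-change analysis is unaffected by either problem.

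**What to change.** In the paragraph on the overall effect, add a continuous-outcome GEE for the within-person analysis. Divide each pre-to-post change by that measure's baseline SD, sign it so that positive means better, and cluster on person. Base the pooled inference on the mean standardized change with its 95% CI against 0. Keep the 0.5 SD responder proportion with its CI as a descriptive summary, state which SD defines the cut, and drop the comparison with 20%. If a pooled continuous analysis was already intended behind the SRM of 0.38, say so and tie the power statement to it.

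The cost is a few sentences and one extra model on data already collected, with no added participants, visits or tests. The small downside is a pooled figure in SD units, which is less intuitive than a proportion; the proportion remains beside it.

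### The design effect of 1.8 multiplies 30 people (54) where it should divide 150 responses (83), and the 28% responder threshold does not follow from 54; the consequence is minor

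*Combined protocol and SAP*

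**What the plan says.** All of this is in the protocol's Analysis and Sample Size section, under Details of Statistical Analysis.

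- The overall effect is to be based "on the proportion of individuals who improved at least 0.5 SD on one of the cognitive outcome measures". For the GEE, however, "The outcome will be the binary response for each of the five cognitive outcomes", and the estimate is a responder proportion adjusted for non-independence.
- On information gained: "Having five outcome measures increases the number of observations available for analysis by a factor of 1.8, termed the design effect". On its form: "The design effect (22) is a function of the number of measures (here m-1) and the correlation between measures (estimated at 0.2".
- On the result: "Hence the number of observations effectively available for analysis is 30 x 1.8 or 54".
- On precision at that size: "the 95% CI will exclude a low responder proportion (20%) as long as the responder proportion is greater than 28" (percent). An online calculator is cited, but no interval method is named.
- For 30 treated people against 100 concurrent controls, the same device recurs: "with five outcome measures, the effective sample size is inflated by the design effect of 1.8". The detectable effect is given as 0.4 SD at 80% power. This comparison is introduced as "for exploratory purposes, (ii) a between group comparison".

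**The concern.** A design effect measures what correlation costs. If responses from one person are correlated, the mean of many responses is less precise than the same number of independent responses would give. The protocol uses it as a gain applied to the number of people, so that more redundant measures would seem to supply more information.

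The threshold is a second and independent problem. It is tied explicitly to the effective sample of 54, so it can be checked on the protocol's own inputs whatever one thinks of how 54 was reached. At stake is whether the stated planning precision for the responder analysis can be relied on. That analysis is offered as the more interpretable summary of treatment impact.

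**Working it through.** **Inputs (Analysis and Sample Size).** n = 30 people; m = 5 measures (B-CAM, SART, Tower of London, DEX, PDQ); ρ = 0.2; reference proportion 20%; 95% interval, read as two-sided (z = 1.96); stated threshold 28%.

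**Step 1: reproduce the protocol's figure.** 1 + (m − 1)ρ = 1 + 4 × 0.2 = 1.8, and 30 × 1.8 = 54. Both reproduce as arithmetic.

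**Step 2: apply the factor to the responses.** The GEE uses 30 × 5 = 150 binary responses. Effective number = nm/[1 + (m − 1)ρ] = 150/1.8 = 83.3. The two limits show which form is right:

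| ρ | Protocol form, 30(1 + 4ρ) | Divided form, 150/(1 + 4ρ) |
|---|---|---|
| 0 (independent) | 30 | 150 |
| 0.2 | 54 | 83 |
| 1 (fully redundant) | 150 | 30 |

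Five independent measures cannot be worth only one, and five identical measures cannot be worth five.

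**Step 3: check 28% at the stated 54.** A Wilson interval excludes 20% when the observed proportion exceeds 0.2 + 1.96√(0.16/n). At n = 54 this is 0.2 + 0.107 = 30.7%. The Wald threshold is 32.5%. Lower 95% limits at attainable counts:

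| Count | Proportion | Wilson | Wald | Exact |
|---|---|---|---|---|
| 16/54 | 29.6% | 19.1% | 17.5% | 18.0% |
| 17/54 | 31.5% | 20.7% | 19.1% | 19.5% |
| 18/54 | 33.3% | 22.2% | 20.8% | 21.1% |

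At exactly 28% the lower limit is 17.8% (Wilson) or 16.0% (Wald). One-sided 95% limits give thresholds of 29.0% to 30.3%, so they do not produce 28% either. A 28% threshold needs an effective number of 0.16 × (1.96/0.08)² = 96 (Wilson) or 0.28 × 0.72 × (1.96/0.08)² = 121 (Wald). Neither number is in the text.

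**Step 4: threshold at the corrected number.** At 83.3, Wilson gives 0.2 + 1.96√(0.16/83.3) = 28.6%, or about 29%.

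**Step 5: the scale of ρ.** The protocol does not say whether 0.2 is the correlation between the responder indicators or between the underlying changes. Suppose it describes normally distributed changes cut so that 20–30% respond (an assumption). The binary correlation is then about 0.11–0.12, the design effect about 1.42–1.48, the effective number about 102–106 and the Wilson threshold 27.6–27.8%.

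**Step 6: which proportion.** The effective number belongs to the proportion averaged over five outcomes. The proportion of people improving on at least one measure has n = 30, and 20% means something different there. If each of five independent measures had 20% responders, 1 − 0.8⁵ = 67% of people would improve on at least one. With changes correlated at 0.2 (equicorrelated normal illustration), it would be about 60%.

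**The case against.** The strongest reply is that little turns on this. The sample is 30 either way, the GEE estimates the correlation from the data, and the interval finally reported owes nothing to the planning figure. At the protocol's own correlation the inversion understates the information, and the corrected threshold lands within a point of 28%. All of that stands, and it limits the weight of the point. It does not rescue the text, because 54 is not the effective number under either reading of ρ and 28% is not the threshold at 54.

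The reply also holds that 83 and 29% should not be presented as the only correct values, since the scale of ρ is unstated. That stands too. On the continuous reading the threshold is about 28%, though at an effective number near 104 and not at 54.

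Two stronger readings are tempting, and the documents do not support them. A reader might infer that the formula misleads in the optimistic direction. That would require a correlation above about 0.31, where 30(1 + 4ρ) overtakes 150/(1 + 4ρ). The protocol gives only 0.2, and Clinical Significance says that the pilot's results, not this formula, will inform a full trial.

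A reader might also infer that 0.4 SD between groups should become 0.35 SD, the value from 150/1.8 = 83 against 500/1.8 = 278. That needs all five measures in the controls. The controls are described as assessed in the main study, while the Procedure section lists SART, Tower of London and DEX as sub-study tests that may be done at a separate visit. If controls had only two measures (an assumption), the effective numbers would be 60/1.2 = 50 and 200/1.2 = 167, and the detectable effect about 0.45 SD. The stated 0.4 SD lies between these values and is not claimed as an error.

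**Conclusion.** Two statements are wrong as written, with minor consequence. The design effect is applied in the wrong direction: 54 should be 83 if ρ = 0.2 is the correlation between binary responses, or about 102–106 if it is the correlation between continuous changes. The 28% threshold also does not follow from the stated 54, where it would be about 31% to 33% depending on the interval method. The second error holds on the protocol's own inputs.

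The figure of 83 assumes an exchangeable correlation, complete data on all five measures and one common responder proportion. Nothing here shows that the trial is too small, that the GEE is the wrong model or that the reported interval would be invalid.

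**What to change.** In the responder paragraph, replace the 54 with: 30 × 5/(1 + (5 − 1) × ρ) = 150/1.8 = 83, taking ρ = 0.2 as the correlation between the binary responses. Restate the threshold as about 29% (Wilson). If 0.2 was meant for the continuous changes, say so and give an effective number of about 102–106 and a threshold of about 28%. Add a sentence that this number and threshold apply to the GEE-averaged proportion over the five outcomes, and not to the proportion of individuals improving on at least one measure, where n = 30.

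In the between-group paragraph, change the inflation wording to the same divide-by-design-effect form, counting only the measures actually available in the controls. Do not substitute 0.35 SD for the stated 0.4 SD.

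The cost is protocol text only, with no change to the sample size, the GEE model or the reported interval.
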